- Changes in concomitant medications, adverse events, compliance to offloading, will be recorded.
- If ulcers heal sooner than 8 weeks, the subject will be assessed the following week. Ulcer healing is defined by 100% epithelization as determined by the clinician. The subject with healed ulcer will also return for follow-up visits Weeks 9, 16, 20.

NOTE: if ulceration remains open after 8th application – then will switch back to standard of care therapy (if budget allows, may consider extending graft course).

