6 STATISTICAL DESIGN

Measures:

Measures will be collected at baseline, weekly thereafter, with primary endpoint of complete healing at Week 12, and final secondary endpoint measurement at Week 20. The ulcer will be assessed weekly and will be treated as described above. A designated inter-observer will be at each of the testing sites, (blinded to the treatment of the subjects) which will perform all measurements. The following measurements will be taken: size (surface area calculation), photos (digital includes ruler) and complete foot ulcer assessment (description of ulcer/characteristics), before and after debridement. Subjects where ulceration healed earlier than Week 12 will have follow-up assessment one week after healing, then at Week 12 and 20. If ulcerations healed after 12 weeks, then the subjects will be assessed at one week after healing and at Week 20. There will be 4 follow-up visits (Weeks 17, 20, 24, 28), assessed every 4 weeks for a total of 16 weeks.

During the study, if ulceration appears to be infected as determined by clinical presentation characterized by the presence of two or more signs of inflammation,³ the clinician will follow the protocol of obtaining wound culture for microbiology, radiographs, blood work (CBC, chemistry panel, sedimentation rate, and C-reactive protein), and treatment immediately with appropriate antibiotics. Subjects with infected ulcers will be withdrawn from study and investigators will be notified. In addition, adverse events will be well documented and treated per protocol, and subjects will be withdrawn from study.

Clinical Outcomes:

- The percentage of subjects that have complete closure of ulceration by Week 12 and Week 20. Complete healing will be defined as full re-epithelialization with no drainage, or callus formation and remains closed after 1 week of wound closure.
- Rate of wound healing to achieve complete closure. Weekly measurements of surface area will be recorded on a grid marked acetate sheet, using a metric ruler to determine length and width of the wound.
- A diabetic foot ulcer assessment form will be filled out at weekly follow-up visits, that describes characteristics of ulceration including peri-ulcer erythema, wound margins, fibrin, granular tissue, peri-ulcer pruritus, edema and location, pain, amount of drainage and type, amount of epithelialization, pain level, depth, and bioburden.

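### Sections 4.3.3 to 4.3.5 state a looser, clinician-called healing rule that conflicts with the Section 6 closure definition, and the SAP carries over neither the definition nor the assessor

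*Combined protocol and SAP*

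**What the plan says.** **Healing rule in the procedures.** Section 4.3.3 (Weeks 1 to 15) states: "Ulcer healing is defined by 100% epithelization as determined by the clinician". Section 4.3.4 (Week 16) and Section 4.3.5 (Weeks 17 to 28, which include the Week 20 visit) use the same criterion and also name the clinician as judge.

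**Healing rule for the endpoint.** Section 6, under Clinical Outcomes, names the outcome: "The percentage of subjects that have complete closure of ulceration by Week 12 and Week 20". The same bullet continues: "Complete healing will be defined as full re-epithelialization with no drainage, or callus formation and remains closed after 1 week of wound closure".

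**Assessor.** Section 3 says that the investigator or clinician will be able to tell the two products apart. To avoid assessment bias, it gives every follow-up evaluation of the wound to an inter-observer blinded to treatment, with another clinician applying the treatment afterwards. Section 6 gives that blinded observer all measurements, including the full ulcer assessment.

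**Visits after healing.** Section 4.3.3: "If ulcers heal sooner than 8 weeks, the subject will be assessed the following week", and "The subject with healed ulcer will also return for follow-up visits Weeks 9, 16, 20". Section 6: "Subjects where ulceration healed earlier than Week 12 will have follow-up assessment one week after healing, then at Week 12 and 20", and "If ulcerations healed after 12 weeks, then the subjects will be assessed at one week after healing and at Week 20".

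**Timing of the primary endpoint.** Section 6 (Measures) opens "with primary endpoint of complete healing at Week 12", while its Clinical Outcomes bullet says *by*.

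**SAP.** It names wound closure by Week 12 as primary and gives the test. It does not define closure or say who assesses it.

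**The concern.** The primary endpoint is a judged, binary event, so the definition and the assessor decide who counts as a success. Two definitions are in force. An ulcer that is fully epithelialized but carries callus, or that reopens within a week, is healed under 4.3.3 and not healed under Section 6. Staff working from 4.3.3 to 4.3.5 meet only the looser rule, and Week 12 has no endpoint procedure of its own: the section titled Study Endpoint is Week 16.

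The assessor matters for the same reason. The procedures leave the call to a *clinician*, a word that Section 3 also uses for someone who can identify the products. If that is the same person, the call that blinding was meant to protect would be made unblinded.

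Two timing gaps add to this. The visit lists for early healers disagree on whether Week 12 is a listed visit, and a closure first seen at Week 12 cannot pass its one-week check until Week 13.

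**Working it through.** **1. The rules side by side.**

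| Item | Sections 4.3.3 to 4.3.5 | Sections 3 and 6 |
|---|---|---|
| Epithelial cover | Complete | Complete |
| No drainage | Not required | Required |
| No callus | Not required | Required |
| Still closed after 1 week | Not required | Required |
| Who judges | The clinician | Blinded inter-observer for evaluations and measurements; the healed call is not named |
| Visits listed if healed before 8 weeks | Following week; Weeks 9, 16, 20 | One week after healing; Weeks 12, 20 |

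The Section 6 rule contains the 4.3.3 rule plus three further conditions. Every discordant ulcer is therefore healed under 4.3.3 and not healed under Section 6, never the reverse.

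**2. Can the Section 6 rule be scored from the form?** The Ulcer Characteristic Form (Section 8) has an epithelialization item with a fully intact category, and drainage type and amount items with a *none* category. It has no callus item. Section 6's own list of the form's contents omits callus too. Calluses appear in the screening examination (4.3.1), which is not a follow-up record. One of the endpoint criteria therefore has no place on the form.

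**3. Is Week 12 observed?** The Section 4.3 flow chart has ulcer assessment at every visit to Week 15. Section 4.3.3 schedules weekly visits, and the table of contents lists Visit 15 (Week 12) and Visit 16 (Week 13). Section 4.3.3 also says that healed subjects *also* return at its listed weeks. Week 12 status is missing only if that list is read as complete.

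**4. By or at Week 12?** *At* 12 weeks: the objectives in the Protocol Summary and Section 2, and Section 6 (Measures). *By* Week 12: the efficacy outcomes in the Protocol Summary, Section 6 (Clinical Outcomes, Sample Size, Analyses) and the SAP primary outcome. Section 6's visit rules cover ulcers healed earlier than Week 12 and after 12 weeks. For closure first seen at Week 12, the check falls at 12 + 1 = Week 13, and no rule says whether it counts.

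**5. Size.** Inputs from Section 6 (Sample Size Estimation): 50% against 25% closure, significance level 0.05, power 80%, chi-square without continuity correction, 57 per group. Two-sided testing is assumed, since sidedness is not stated.

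- Plan's figure: n = [1.960·√(2·0.375·0.625) + 0.842·√(0.25·0.75 + 0.50·0.50)]² / 0.25² = 57.67, so 58 rounded up. The stated 57 is reproduced to within one subject.
- Power at 57: Φ{[0.25·√57 − 1.960·√(2·0.375·0.625)] / √(0.25·0.75 + 0.50·0.50)} = Φ(0.825) = 79.5%.
- One discordant subject: 1/57 = 1.75 percentage points on that arm's closure rate.

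**6. Illustration only.** Suppose that the planned 50% and 25% were rates under the looser rule, and that a share f of those closures failed the Section 6 rule equally in all arms. The rates become 0.50(1 − f) and 0.25(1 − f), and the same power formula gives:

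| f (assumed) | Rates | Power at 57 per arm |
|---|---|---|
| 5% | 47.5% vs 23.75% | 76.1% |
| 10% | 45% vs 22.5% | 72.5% |
| 20% | 40% vs 20% | 64.8% |

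No value of f is in the documents. If the planned rates already use the Section 6 definition, the change is zero.

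**The case against.** The best defence is that the endpoint is already defined. Section 6 puts its definition in the same bullet as the Week 12 and Week 20 percentages, and the SAP is bound with the protocol, so it need not repeat it. The sentence in 4.3.3 sits among visit-scheduling instructions, in a section where product is applied until healing, so a simple clinic-side call has a use there. The return visit a week later even serves the one-week check. Most of this stands: Section 6 very probably governs, and it would be wrong to call the endpoint undefined.

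A reader might also infer that unblinded clinicians will score the endpoint. The documents do not support that. Section 3 gives follow-up evaluations to the blinded observer and has *another* clinician apply the treatment, which suggests that the observer may also be a clinician. Nor do they support the inference that Week 12 is unobserved in early healers, because the weekly schedule probably supplies that visit.

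What the defence does not answer is that 4.3.4 and 4.3.5 repeat the looser rule after the application period, including at the Week 20 endpoint visit. No sentence gives either rule precedence or names who makes the call. The missing callus item, the differing visit lists and the unstated Week 12 counting rule remain on any reading.

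**Conclusion.** The point holds as an internal inconsistency that is wrong as written and should be corrected, with moderate confidence. The plan contains a sound endpoint definition and a blinded assessor, but its procedures state a conflicting rule, its form cannot fully record the definition, and its SAP is silent on both.

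The weight is 1.75 percentage points per discordant subject in an arm of 57. How many such subjects there would be is unknown. A reader might take the power figures above as an expected loss. They are not: they rest on assumed failure rates and on the planned rates having been set under the looser rule, whereas the sample-size text speaks of complete ulcer closure, which is closer to Section 6. They also assume equal failure across arms and concern active treatment against standard care, so they say nothing about assessor bias or about Oasis against Dermagraft.

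The risks of an unblinded call and of missing Week 12 status are conditional on readings that other sections make less likely.

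**What to change.** For endpoint scoring only:

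1. In Section 6 and the SAP, state that Week 12 and Week 20 closure is scored by the Section 6 definition, with the healed or not-healed call made by the blinded inter-observer.
2. In 4.3.3, 4.3.4 and 4.3.5, cross-refer to that definition and assessor for endpoint purposes.
3. Add a callus item to the Ulcer Characteristic Form.
4. State whether the primary endpoint is closure *by* Week 12 or closure present *at* Week 12, and whether closure first seen at Week 12 and confirmed at Week 13 counts.
5. Reconcile the post-healing visit lists in 4.3.3 and Section 6 so that Week 12 status is observed for every subject. Which list is adopted is for the sponsor.

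No treatment rule changes. The cost is wording and one form field, since the blinded observer, the drainage items and Visits 15 and 16 are already planned. The downside is that closure rates may be slightly lower than under the looser wording.

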4.3.3 Treatment Phase (Visits 4 to 18/Weeks 1 to 15)

Subjects will be evaluated and receive treatments on weekly basis (7 days +/- 2 days).

Appointments will be made as determined by investigator at each VA facility.

- At each visit, vital signs will be obtained and recorded.
- The ulcer will be assessed – visual inspection – complete ulcer characteristics form (see appendix).
- If there is concern for infection after evaluation of ulcer, then a confirmatory bacterial culture will be obtained (deep swab culturette or tissue specimen/biopsy). Radiographical xrays and blood work (CBC, ESR, CRP, and Chem) may also be performed if deemed necessary by investigator clinician.
- Next, a digital image will be taken one image before debridement and one image immediately after debridement (camera will capture dimensional size of ulcer). The images will be stored on a central server, with unique identifier as well as loaded on CPRS Vista imaging.
- Surgical debridement of ulcer will be performed using curette or blade. Clinician should debride wound to promote mild bleeding from ulcer site and removal of necrotic or fibrinous tissue and excess hyperkeratotic margins if possible. Clinician may use lidocaine topical jelly/ointment if ulcer is too tender to debride.
- All wound beds will be cleaned gently with normal saline 0.9%.
- Application of treatments:
 - Standard (Conventional) Therapy:
Application of non-adhesive dressing (Adaptic® or Mepitel®), Iodosorb® gel over wound bed, covered by dry gauze dressings.

Oasis®:

The Oasis® matrix will be applied on the wound (cut to size using scissors), moistened with normal saline to assure adherence to wound bed, then apply non-adhesive dressing (Adaptic® or Mepitel®), moist sterile gauze, dry and gauze dressings. Up to 8 weekly applications will be applied to wound until healed.

Dermagraft®:

The Dermagraft® will be thawed as directed by the manufacturer, then under sterile technique Dermagraft® will be cut to size of wound using scissors,

covered with non-adhesive coverage (Adaptic® or Mepitel®), moistened sterile gauze and dry dressings. Up to 8 weekly applications will be applied to wound until healed.

- Offloading devices:
 - Plantar foot ulcers – offload with post operative style shoe (with plastazote cut out (perature or extravasation) as necessary to offload ulcer pressure area.
 - Heel ulcers – use multi-podus splint or Rooke boot.

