4.3.5 Follow-Up Phase (Visits 20 to 23/Weeks 17 to 28)

- The ulcer will be assessed – visual inspection – complete ulcer characteristics form (see appendix). Determine if reaches 100% epithelization by clinician.
- Digital imaging of ulcer location, if remains non-healing then 2 images to be obtained prior to and after surgical debridement.
- Surgical debridement of ulcer if not healed, will be performed using curette or blade and standard therapy.
- Changes in concomitant medications, adverse events, compliance to offloading, will be recorded.

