5 ADVERSE EVENTS

All adverse events reported spontaneously by the subject/or in response to questioning or observation by the investigator will be recorded.

Reporting of Adverse Events:

The Investigator will be responsible for assessing the relationship of the adverse event to the investigational product, and the seriousness and expectedness of the adverse event at the time of occurrence. All adverse events that occur during the trial will be documented.

AE's/SAE's reported during the study, or SAE's reported within 30 days of the end of the study, should be followed to resolution of the AE/SAE or, within thirty days from the end of the study, a further and final assessment of the outcome should be made. Each AE will be categorized as "serious" or "not serious" based on the definition of an SAE. An SAE is defined as an AE resulting in at least one of the outcomes described in the sections below.

The severity of AEs will be classified as "mild", "moderate", or "severe", based on the following definitions:

- Mild: Awareness of sign, symptom, or event, but easily tolerated; does not interfere with usual daily activities or tasks.
- Moderate: Discomfort enough to cause interference with usual daily activity; may warrant therapeutic intervention.
- Severe: Incapacitating; inability to perform usual activities and daily tasks; significantly affects clinical status; requires therapeutic intervention.

Adverse events will be assigned a relationship (causality) to the study products. The Investigator will be responsible for determining the relationship between an AE and the study product. The type of event, organ system affected, and timing of onset of the event will be factors in assessing the likelihood that an AE is related to the treatment. Relationship of AEs to study products will be classified as follows:

- Not Related: No relationship exists between the AE and the treatment. The event is attributed to a pre-existing medical condition or an intercurrent event unrelated to the study product.
- Possibly Related: Follows the treatment, but may have developed as a result of an underlying clinical condition or treatments/interventions unrelated to the study product.
- Probably Related: Follows the treatment, but is unlikely to have developed as a result of the subject's underlying clinical condition or other treatment or other interventions.
- Definitely Related: Follows the treatment and physical evidence shows a convincing relationship to the treatment.

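### Sections 4.3.3 and 6 give conflicting reduced visit schedules after healing, one without a Week 12 visit, and the last follow-up week is inconsistent, so planned adverse-event contacts depend on healing

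*Combined protocol and SAP*

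**What the plan says.** Section 4.3.3 has subjects seen weekly through Week 15. For an ulcer that heals in under 8 weeks it sets an assessment the following week and adds: "The subject with healed ulcer will also return for follow-up visits Weeks 9, 16, 20". It gives no rule for healing at Week 8 or later.

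Section 6 (Measures) has a different rule: "Subjects where ulceration healed earlier than Week 12 will have follow-up assessment one week after healing, then at Week 12 and 20". For later healing it says: "If ulcerations healed after 12 weeks, then the subjects will be assessed at one week after healing and at Week 20".

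The flow chart in Section 4.3 marks ulcer assessment and adverse-event review in every visit column up to Visits 20-23, with no condition on healing. Section 6 likewise states without condition: "There will be 4 follow-up visits (Weeks 17, 20, 24, 28), assessed every 4 weeks for a total of 16 weeks".

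The end of follow-up is not given consistently. The flow chart, Section 4.3.5 and Section 6 (Measures) run to Week 28. The Protocol Summary gives up to 22 weeks per subject including 2 weeks of screening. The timeline in Section 6 keeps subjects unhealed at Week 12 in the study until Week 20.

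On how events are found, Section 5 says: "All adverse events reported spontaneously by the subject/or in response to questioning or observation by the investigator will be recorded".

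**The concern.** There are two consequences.

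The first is for efficacy data. Closure by Week 12 is the primary endpoint, and ulcer recurrence at 20 weeks is analysed (Section 6 and the SAP). A subject on the 4.3.3 schedule has no planned visit between Weeks 9 and 16. A re-opening first seen at Week 16 could not be dated before or after Week 12 from the scheduled assessments. Section 6 words the primary endpoint both as healing at Week 12 and as closure by Week 12. If healing at Week 12 is meant, such a subject has no planned observation at the endpoint.

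The second is for safety data. Questioning and observation need a contact. If contacts become sparser once an ulcer heals, their number depends on a post-randomisation outcome that the plan expects to differ between the product arms and standard care. The counts of infection, osteomyelitis, acute Charcot and adverse effects in Section 6 are the only safety outcomes listed there, and Section 5 sets up no monitoring board. A difference in these counts between a product and standard care could then partly reflect how often subjects were seen.

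**Working it through.** **1. The schedules side by side.**
- Section 4.3.3 (healed before 8 weeks): following week, then Weeks 9, 16, 20.
- Section 6 (healed before Week 12): one week after healing, then Weeks 12, 20.
- Flow chart: every visit, with no healing condition.

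Apart from the one-week check, the two reduced schedules share only Week 20. Weeks 9, 12, 16 and 20 are already visits for everyone. Naming them for healed subjects has an effect only if the other visits drop out, and I read both rules that way.

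**2. End of follow-up.** The Protocol Summary's 22 weeks is 2 screening + 8 treatment + 12 follow-up, which ends at Week 20. The timeline also gives Week 20. The flow chart, Section 4.3.5 and Section 6 (Measures) give Week 28.

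**3. The plan's own figure.** The plan states no number of safety contacts. The closure rates (50% in each product arm, 25% on standard care) come from the sample-size paragraph in Section 6, which gives 57 per group. With two-sided alpha 0.05 (sidedness is not stated), 80% power and no continuity correction:

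n = [1.960 × √(2 × 0.375 × 0.625) + 0.842 × √(0.25 × 0.75 + 0.50 × 0.50)]² / 0.25² ≈ 57.7, rounded up to 58.

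This is within one of the stated 57, so the rates are the ones the plan was built on.

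**4. Planned contacts from Week 1.** Let U be the visits of an unhealed subject and H those of a subject healed at week h.
- Full schedule: Weeks 1-17 plus 20, 24, 28, so U = 20. If everyone ends at Week 20, U = 18.
- Section 4.3.3: Weeks 1 to h+1, then 9, 16, 20. For h = 4, H = 5 + 3 = 8. For h = 6, H = 7 + 3 = 10.
- Section 6: Weeks 1 to h+1, then 12, 20. For h = 4, H = 5 + 2 = 7. For h = 6, H = 7 + 2 = 9. For h = 10, H = 11 + 2 = 13.
- If healed subjects also attend Weeks 17, 20, 24 and 28, add 3 to H, since Week 20 is already counted.

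Mean per arm = p × H + (1 − p) × U, with p = 0.50 (product) or 0.25 (standard care). All healers are assumed to heal at week h, the rest keep the full schedule, and nobody withdraws.

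Reading A: everyone ends at Week 20. Reading B: everyone attends through Week 28. Reading C: healed subjects end at Week 20 and unhealed at Week 28. The documents do not state Reading C; it is shown only as an outer bound.

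| Schedule, h | A: product vs standard (ratio) | B | C |
|---|---|---|---|
| 4.3.3, h = 4 | 13.00 vs 15.50 (0.839) | 15.50 vs 17.75 (0.873) | 14.00 vs 17.00 (0.824) |
| 6, h = 4 | 12.50 vs 15.25 (0.820) | 15.00 vs 17.50 (0.857) | 13.50 vs 16.75 (0.806) |
| 4.3.3, h = 6 | 14.00 vs 16.00 (0.875) | 16.50 vs 18.25 (0.904) | 15.00 vs 17.50 (0.857) |
| 6, h = 6 | 13.50 vs 15.75 (0.857) | 16.00 vs 18.00 (0.889) | 14.50 vs 17.25 (0.841) |
| 6, h = 10 | 15.50 vs 16.75 (0.925) | 18.00 vs 19.00 (0.947) | 16.50 vs 18.25 (0.904) |

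The ratios run from 0.806 to 0.947, or about 5-19% fewer planned contacts in a product arm. Without Reading C the range is 0.820 to 0.947, about 5-18% fewer. Most of the gap comes from leaving the weekly visits: for Section 6 with h = 6 it is 2.00 contacts under B and 2.75 under C.

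**5. After the fix.** With one set of review dates for every subject, H = U and the ratio is 1.00.

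**The case against.** A reader might infer that healed subjects leave the study at Week 20 while unhealed subjects are followed to Week 28. That would give mean follow-up of 0.5 × 20 + 0.5 × 28 = 24 weeks in a product arm against 0.25 × 20 + 0.75 × 28 = 26 on standard care, with late events in healed subjects never sought. The documents do not support this. The Week 17-28 visits carry no healing condition in the flow chart or Section 6. Section 4.3.5, on those same visits, says: "Surgical debridement of ulcer if not healed, will be performed using curette or blade and standard therapy". That condition implies that healed subjects attend too. The timeline points the other way, keeping subjects unhealed at Week 12 only until Week 20. Follow-up length is inconsistent for everyone and is not shown to differ by healing status.

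Other objections also carry weight:
- Fewer visits need not mean fewer recorded events. Spontaneous reports are recorded, a later visit can pick up earlier events, and serious events are reportable throughout (although to a final evaluation for which Section 5 gives no week).
- A healed subject has no open wound, debridement or applications, so true risk may be lower.
- Both products are expected to reach 50% closure, so the cellular versus acellular comparison, the primary objective, has no expected imbalance. No between-arm safety test is planned.
- The count leaves out subjects who heal after Week 12, who also move to fewer visits. It also leaves out withdrawal for infection or adverse events (Section 6) and discontinuation of non-responders (Section 3). Those losses may fall mainly on unhealed subjects and could shrink or even reverse the gap.
- Thinner follow-up after healing is a defensible choice in itself.

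These points limit what can be said about bias. They do not remove the conflict between the schedules or the missing Week 12 visit in Section 4.3.3. Section 6 does provide a Week 12 visit, but nothing says which section governs.

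**Conclusion.** The concern holds as an inconsistency with a modest effect on how often subjects are seen. The two post-healing schedules conflict with each other and with the flow chart, Section 4.3.3 omits the primary time point, and the last follow-up week is either 20 or 28 depending on the section.

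On the plan's own closure rates, each product arm would have about 5-19% fewer planned adverse-event contacts than standard care. This rests on weekly visits stopping at healing, healing at Weeks 4-10 and no withdrawals. The top of the range needs the unsupported split in follow-up; without it the upper figure is about 18%.

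It would go too far to conclude that a product will look safer than standard care. The documents give no event rates, and under-detection cannot be separated from a real fall in risk after healing. The size of any adverse-event bias cannot be computed. The point should be corrected, chiefly because correction is cheap and also protects the Week 12 and recurrence data.

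**What to change.** Reconcile the Protocol Summary, the Section 4.3 flow chart, Sections 4.3.3 and 4.3.5, and Section 6 (Measures and timeline) into one visit schedule and one last follow-up week for all randomised subjects. The sponsor has to decide which last week is intended.

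Within that schedule:
- include a Week 12 ulcer assessment for every subject, healed or not;
- carry out adverse-event review on the same dates in every subject, by brief telephone contact where no clinic visit is due;
- report adverse events by arm over that common window.

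The cost is protocol wording and a few more contacts by existing staff. The recorded event count in the product arms may rise slightly because healed subjects are asked more often.
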